Optical coherence tomography for microvascular lung vessels obstructive thromboinflammatory syndrome assessment in patients with COVID-19: an exploratory study.

Protocol Version 1.0 _ 06/May/2020

Promoter/P.I.: Dr. [name]

Signature:

Background

Severe acute respiratory syndrome coronavirus 2 (SARS- CoV-2) infection represents a pandemic emergency of dramatic proportions. The clinical course of SARS-CoV-2 infection often meets the criteria for acute respiratory distress syndrome (ARDS), with progressive severity ultimately leading to a rapid death. It appeared that the progressive worsening lung function of patients infected with SARS-CoV-2 was potentially driven by host immune response. SARS-CoV-2 replication in lung epithelial cells causes direct cellular damage and release of pro-inflammatory alarmins from dying cells. The successive complement system activation causes massive local release of pro-inflammatory cytokines and consequent severe collateral tissue injury and massive vascular endothelial and alveolar epithelial cell damage and microvascular thrombosis. Functional implications of this peculiar ARDS pathogenesis include a progressive worsening of ventilation/perfusion imbalances and a loss of hypoxic vasoconstriction reflexes, with a marked component of microvascular pulmonary thrombosis, as suggested by lactate dehydrogenase and Ddimer elevations. In the late stages of ARDS, the progression of endothelial damage with microvascular thrombosis can spread locally in the lung and potentially extends the systemic inflammatory reaction involving the microvascular bed of the kidneys, brain and other vital organs¹. A new mechanism of lung damage was recently proposed, with dramatic alveolar endothelial damage leading to a progressive endothelial pulmonary syndrome with microvascular thrombosis and suggests MicroCLOTS (microvascular COVID-19 lung vessels obstructive thromboinflammatory syndrome) as an atypical ARDS working hypothesis¹.

In fact, thromboembolic events rate in COVID-19 patients appears not negligible², and a prophylactic utilization of low molecular weight heparin (LMWH) should be considered³.

Several biomarkers are under investigation to better determine the risk of thromboembolic events and to determine the patients who could benefit more of a prophylactic therapy with LMWH. Among others, D-Dimer is often elevated in COVID-19 patients^{3,4} and should be used as the most important

parameter for thromboembolic risk stratification, together with other inflammation index like C-reactive-protein, interleukin 6 (IL-6) and ferritin.

Nevertheless, a not negligible part of patient with COVID-19 pneumonia presents high D-dimer level with computed tomography (CT) scan negative for pulmonary embolism. Despite these patients could presents pulmonary microvascular thrombosis (MicroCLOTS)¹, it has never been proven and an aggressive anticoagulant treatment is currently not utilized.

A diagnostic technique more sensible than the CT scan on the small pulmonary arteries could theoretically allow the detection of MicroCLOTS thus justifying a more aggressive anticoagulant regimen.

Optical coherence tomography

The optical coherence tomography (OCT) is a near-infrared light source-based imaging technique with a resolution of 10–20 µm⁵. It acquires longitudinal sequences of cross-sectional images (100 frames/s) in a blood-free environment, resulting in sharp border definition between lumen and vessel wall. It is routinely used in percutaneous coronary intervention (PCI) to better characterize vessel anatomy, as well as ascertainment of full stent deployment and expansion⁶.

Moreover, OCT has been shown to have a good correlation with histology even in the evaluation of pulmonary artery morphology, particularly in the evaluation of pulmonary arterial wall thickness⁷. Furthermore, OCT has been used to better characterized distal Type Chronic Thromboembolic Pulmonary Hypertension⁸, and to guide its treatment with percutaneous transluminal pulmonary angioplasty⁹.

Hong et al¹⁰ evaluated with OCT three patients who were highly suspected for peripheral pulmonary arteries thrombi but had negative CT scan for pulmonary embolism. Thrombi were found in most of imaged vessels in these patients. Red and white thrombi can be differentiated, according to features of the thrombus on OCT images. After anticoagulation treatment, these patients' symptoms and hypoxemia improved. Repeated OCT imaging showed that most thrombi disappeared or became smaller.

OCT was also used in evaluation of pulmonary arterial vasculopathy in Systemic Sclerosis, showing an unexpected evidence of pulmonary artery thrombus formation in 19% of systemic-sclerosis patients with pulmonary arterial hypertension¹¹.

There are sufficient data showing OCT to be a useful tool to identify intravascular thrombi in patients with chronic thromboembolic pulmonary hypertension, together with an increase in vessel wall thickness in most patients with pulmonary hypertension^{12,13}.

Aim of the study

To evaluate by intravascular OCT study the presence of microvascular pulmonary thrombosis in patients with COVID-19, high D-dimer levels and contrast CT scan negative for pulmonary thrombosis. We'll also evaluate the extension of microvascular pulmonary thrombosis in patients with contrast CT scan positive for pulmonary embolism in areas where contrast CT scan was negative.

Inclusion Criteria (part A)

- Age ≥ 18
- Severe pulmonary coronarvirus disease 19 (COVID 19) with suspect for MicroCLOTS
 (microvascular COVID-19 lung vessels obstructive thromboinflammatory syndrome) AND
- Contrast CT scan negative for pulmonary thrombosis AND
- D-Dimer $> 10 \text{ mcg/mL } \mathbf{OR}$
- 5 < D-dimer < 10 mcg/mL and either C Reactive Protein (CRP) > 100 mg/dL or IL-6 > 6 pg/mL or ferritin > 900 ng/L

Inclusion Criteria (part B)

- Age ≥ 18
- Severe pulmonary coronarvirus disease 19 (COVID 19) with suspect for MicroCLOTS (microvascular COVID-19 lung vessels obstructive thromboinflammatory syndrome) **AND**
- Contrast CT scan positive for pulmonary thrombosis

Exclusion Criteria

- Age < 18
- Pregnancy or breastfeeding
- Known allergy to iodinated contrast dye
- Hemodynamic instability
- Glomerular Filtration rate < 30 ml/min
- Active bleeding or absolute contraindication to anticoagulant therapy

OCT procedure

- Femoral vein echo-guided puncture; 6 Fr 11 cm sheath insertion.

- Unfractionated heparin administration (70 100 U/kg) to achieve an activated clotting time (ACT) between 250 and 300 seconds.
- Pulmonary artery cannulation with 5 Fr Multipurpose (MP) catheter (Cordis, Dublin, Ohio) and Storq wire (Cordis).
- Pulmonary artery pressure measurement
- Selective pulmonary artery cannulation and angiography
 - The choice of the pulmonary arteries to be cannulated will be driven by "ground glass" area at CT scan
- 5Fr MP catheter will be changed for 6Fr MP guiding catheter over the Storq wire.
- Storq wire removal and 0.014" Balance wire distally advanced.
- OCT images acquisition
 - In order to remove all the blood, as well as to obtain clear images, iodinated contrast is infused at a flow rate of 5 mL/s over 4 s, at 400 psi of pressure (Acist, Eden Prairie, Minnesota). Automatic pullback at 20 mm/s.
- If needed, blood samples can be taken through Recover catheter (Hexacath, Rueil-Malmaison, France)
- The same procedure will be performed:
 - o on "healthy" (without ground glass appearance at CT scan) area in the same lung
 - o on contralateral lung, both in "ground glass" and "healthy" areas according to CT scan.

PRIMARY ENDPOINT

- Overall safety of OCT procedure in COVID-19 pneumonia patients
- Presence of microvascular pulmonary thrombosis at OCT assessment in COVID-19 patients, both in "ground glass" and "healthy" ventilated areas.

SECONDARY ENDPOINT

- Pulmonary artery vessel anatomy characterization in COVID-19 patients
- Correlations with single trans-thoracic echocardiography (TTE) pulmonary hypertension (PH, estimated systolic pulmonary artery pressure > 35 mmHg) and right ventricular disfunction (RVD: tricuspid annular plane systolic excursion < 17 mm or Doppler tissue imaging S wave < 9.5 cm/sec).
- Dynamic correlations with standard inflammatory, coagulation and tissue damage

Study design, sample size, statistical analysis

The study is an open label, prospective, interventional clinical study of the safety, tolerability and potential diagnostic value of optical coherence tomography for microvascular lung vessels obstructive thromboinflammatory syndrome assessment in patients with COVID-19 pneumonia. This is a proof of concept exploratory study and will be conducted in 10 patients with mild-to-severe

The sample size calculation was designed for safety assessment based on a reference population of last 100 patients who underwent OCT at our Institution for coronary Artery Disease (CAD) in which a rate of SAEs lower than 1% have been recorded (personal communication)

Primary endpoint

ARDS.

As for safety analysis, the number of imaging related complications (expected/unexpected) and serious events (SAEs) (expected/unexpected and/or related/not related) and the percentage of subjects experiencing imaging related event (IRE) and SAEs in the study will be summarized by severity and within body system involved. Narratives will also be presented.

Secondary endpoints

Continuous variables will be summarized with indices of location (i.e. mean or median) and dispersion (i.e. standard deviation or interquartile range), as appropriate. All relevant estimates will be reported with the corresponding 95% Confidence Intervals (CI).

Patients will be censored at study closure, withdrawn of consent or loss to follow-up.

Withdrawal and Premature Termination or Suspension of Study

Investigators may terminate a study subject's participation in the study if:

- Any clinical AE, or other medical condition or situation occurs such that continued participation in the study would not be in the best interest of the subject.
- The subject meets an exclusion criterion, either newly developed or not previously recognized (except those caused by ARDS and SARS-CoV-2 infection), that precludes further study participation.

This study may be suspended or prematurely terminated if there is sufficient reasonable cause. Written notification, documenting the reason for study suspension or termination, will be provided.

Circumstances that may warrant termination include, but are not limited to:

• Determination of unexpected, significant, or unacceptable risk to subjects;

Adverse events (AE)

AE is defined as any untoward medical occurrence in a patient or clinical investigation subject who underwent to a clinical procedure regardless of its causal relationship to the clinical procedure itself. An AE can therefore be any unfavorable and unintended sign (including an abnormal laboratory finding), symptom, or disease temporally associated with the performing of the clinical procedure. The occurrence of an AE may come to the attention of study personnel during the hospitalization period, or during follow up visits and interviews of a study subject presenting for medical care, or upon review by a study monitor.

Each AE will be recorded only once on the "Adverse Event" CRF page, with seriousness and maximum intensity that occurred over the duration of the event. Each event will also be evaluated with respect to causality and actions taken. All AEs will be monitored and recorded throughout the study. For all adverse events that require the subject to be discontinued from the study, the event(s) will be followed until final resolution or stabilization of the event(s).

The Investigator will classify and evaluate each AE as follows:

- Description of event (if the event consists of a cluster of signs and/or symptoms, record a diagnosis [e.g.: "flu"] rather than each sign and symptom)
- Onset date
- Stop date (if resolved)
- Seriousness (see definition of serious adverse events below)
- Intensity ("Mild" [does not interfere with daily activities]; "Moderate" [interferes with daily activities]; "Severe" [prevents daily activities])
- Relationship to study intervention (Not Related, Possibly Related, Probably Related)
- Action taken (None, Required concomitant treatment, Permanent discontinuation of study intervention, Other [explain])
- Outcome (recovered without sequelae, Resolved with sequelae, Ongoing, Unknown, Death)

Serious Adverse Events (SAE)

An SAE is an AE that meets 1 or more of the following criteria:

- Results in death
- Is immediately life-threatening (places the subject at immediate risk of death from the event as it occurred)
- Requires or prolongs in-patient hospitalization
- Results in a persistent or significant disability or incapacity
- Results in a congenital anomaly or birth defect or malignancy
- Is medically important
- Requires medical intervention to prevent permanent impairment or damage

Imaging-related events

Intra-procedural adverse events will be recorded and considered as potential imaging-related events (IRE). IRE will be defined as the occurrence of clinical symptoms (worsening of respiratory failure, requiring invasive mechanical ventilation, hemoptysis), adverse angiographic outcomes (dissection, perforation, vasospasm, thrombus formation, abrupt closure), requiring interruption of the imaging procedure during intra-polmonary imaging and will be routinely registered by the operator. Major peri-procedural adverse events will be also be recorded: death, acute kidney injury, major bleedings, contrast media reaction, access-site related complications.

Fundings: The procedure will be covered by SSN. The other costs (see attached table of costs) will be covered by COVID BIOB funds.

REFERENCES

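### Chronic thromboembolic disease or pulmonary arterial hypertension known before COVID-19 is not excluded, so old thrombus could be counted in the OCT thrombosis endpoint

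*Protocol*

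**What the plan says.** In the Protocol, the background section Optical coherence tomography describes what OCT finds in pulmonary disease other than COVID-19:

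- On chronic thromboembolic pulmonary hypertension: "There are sufficient data showing OCT to be a useful tool to identify intravascular thrombi in patients with chronic thromboembolic pulmonary hypertension". The same sentence continues "together with an increase in vessel wall thickness in most patients with pulmonary hypertension".
- On systemic sclerosis, it reports "pulmonary artery thrombus formation in 19% of systemic-sclerosis patients with pulmonary arterial hypertension".

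The Exclusion Criteria have six items: age, pregnancy or breastfeeding, contrast allergy, hemodynamic instability, low glomerular filtration rate and, last, "Active bleeding or absolute contraindication to anticoagulant therapy". None concerns earlier thromboembolic disease or pulmonary hypertension. The inclusion criteria do not screen for them either. Part A requires a contrast CT negative for thrombosis plus D-dimer and inflammatory thresholds. Part B requires a positive contrast CT, with no D-dimer threshold and no distinction between acute and chronic thrombus.

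The second primary endpoint is "Presence of microvascular pulmonary thrombosis at OCT assessment in COVID-19 patients", in ground-glass and in healthy areas alike. On size and design: "This is a proof of concept exploratory study and will be conducted in 10 patients". No comparison group is described.

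**The concern.** The protocol names two conditions other than COVID-19 in which OCT shows thrombus, then leaves both out of its exclusions. The endpoint is a simple presence or absence, so it cannot tell thrombus that formed during COVID-19 from thrombus that was already there.

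This matters because of how the result would be read. The Background says that MicroCLOTS has not been proven and that detecting it could support more intensive anticoagulation. With 10 patients, one wrongly attributed case could change the report from not seen to seen.

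A separate and smaller effect concerns wall thickening. Pulmonary hypertension that predates COVID-19 would influence the secondary endpoints on vessel anatomy and on correlation with echocardiographic pulmonary hypertension. The latter is taken from a single echocardiogram, with no pre-COVID baseline required.

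**Working it through.** The protocol gives no figure that tests this point. Its sample size of 10 is said to rest on safety, so it is taken here as given.

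**Step 1. Does anything in the plan close the gap?**

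- *Part A negative CT.* It removes thrombus that CT can see. The study's premise is that OCT may see what CT misses, and the background cites a three-patient series with negative CT in which OCT found thrombi in most imaged vessels. The filter is partial.
- *Part B positive CT.* Chronic thrombus visible on CT could satisfy this criterion. The Aim then looks at areas where CT was negative, and OCT thrombus there would count.
- *Suspected MicroCLOTS.* This is required in both parts but is not defined operationally.
- *Red versus white thrombus.* The background says OCT can tell them apart, but no endpoint uses the distinction.
- *Healthy areas.* They are imaged, but thrombosis there also counts as presence.

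None of these separates old from new thrombus.

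**Step 2. Chance of enrolling such a patient.** Inputs: n = 10 (Study design section) and q, the share of candidates with one of these conditions. The documents do not give q, so 2%, 5% and 10% are assumptions. The formula is 1 − (1 − q)^10.

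**Step 3. Chance that such a patient also shows thrombus.** Added input: the background's 19%, which is for pulmonary arterial hypertension in systemic sclerosis. The formula is 1 − (1 − 0.19q)^10.

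| Assumed q | At least one enrolled | At least one with thrombus at 19% | Average shift in the rate, at most (0.19q) |
|---|---|---|---|
| 2% | 1 − 0.98^10 = 18.3% | 1 − 0.9962^10 = 3.7% | 0.38 points |
| 5% | 1 − 0.95^10 = 40.1% | 1 − 0.9905^10 = 9.1% | 0.95 points |
| 10% | 1 − 0.90^10 = 65.1% | 1 − 0.981^10 = 17.5% | 1.9 points |

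For chronic thromboembolic disease the documents give no thrombus rate. If every such patient showed thrombus, which is an assumed ceiling, the third column would rise to equal the second.

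**Step 4. Effect of one case.** Each patient is 1/10, or 10 percentage points. Exact (Clopper-Pearson) 95% intervals:

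- 0/10: 0 to 30.8% (upper limit 1 − 0.025^(1/10) = 0.308)
- 1/10: 0.3% to 44.5%

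The shift is at most 10 points per case, because a patient with both old and new thrombus would have counted anyway.

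**The case against.** The strongest reply is that this is a 10-patient exploratory study whose stated aim is to look for thrombosis in patients with COVID-19, not to prove that COVID-19 causes it. Broad eligibility is defensible for that aim, and with 10 patients any relevant history can be described case by case. The route to a miscounted case is also narrow: severe COVID-19, suspected MicroCLOTS and, in part A, a negative contrast CT are all needed. Each patient also provides a within-patient contrast between ground-glass and healthy areas in both lungs, and pulmonary artery pressure is measured during the procedure.

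Much of this stands, and it limits the point. It does not remove it, because nothing commits the study to recording or reporting such a history, and thrombosis is a primary endpoint.

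A reader might also infer more than the documents support:

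- *That old disease will be counted.* It can be counted only if such a patient is enrolled, and the prevalence is unknown.
- *That wall thickening inflates the thrombosis rate.* It does not enter that count; it bears only on the secondary endpoints.
- *That the protocol says an earlier pulmonary embolism shows on OCT.* The background does not name previous embolism as such a cause. In the three-patient series, most thrombi disappeared or shrank after anticoagulation.
- *That 18%, 40% and 65% are the chances of a false case.* They are the chances of enrolling such a patient.
- *That attribution rests wholly on eligibility.* The within-patient contrast and the pressure measurement give some information, though neither settles the matter.

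**Conclusion.** The point holds in a limited form. The criteria admit patients with known chronic thromboembolic disease or pulmonary arterial hypertension, the protocol's own background says OCT can show thrombus in both, and the endpoint has no means of setting that thrombus apart. Eligibility is fixed in the protocol, so this is not a detail left to an analysis plan.

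Its size is uncertain. It rests on an assumed prevalence, on independence between patients, and on a 19% rate borrowed from one of the two conditions. Over the assumed range, a miscounted case is more likely absent than present at the 19% rate, and the average shift in the thrombosis rate is under 2 points. The weight lies in the single-case effect, up to 10 points in a sample of 10. Severity is low to moderate; the change is worth making because it is cheap.

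**What to change.** Add one exclusion criterion, checked from history and existing records: chronic thromboembolic disease or pulmonary arterial hypertension (including that associated with systemic sclerosis) known before the COVID-19 episode. Known previous pulmonary embolism can be added as a precaution; that item rests on the absence of any rule separating old from new thrombus, not on the background.

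If the sponsor prefers not to exclude, flag these patients at screening. Report them separately from the thrombosis, vessel-anatomy and pulmonary-hypertension endpoints, and keep them in the safety endpoint. The reporting rule can sit in the protocol or in an analysis plan, provided it is fixed before the images are read.

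The cost is one line in an amendment and no new test. Excluding may lose a few candidates; flagging loses none but leaves fewer than 10 patients for the affected endpoints if any are flagged.

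### Part A eligibility: the printed units for ferritin (ng/L) and CRP (mg/dL) put one cut-off below practically every adult value and the other above practically every patient value

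*Protocol*

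**What the plan says.** Part A of the inclusion criteria takes adults with severe pulmonary COVID-19, suspected MicroCLOTS and a contrast CT scan negative for pulmonary thrombosis, by one of two D-dimer routes. Above 10 mcg/mL no further marker is needed. In the lower band a marker is added: "5 < D-dimer < 10 mcg/mL and either C Reactive Protein (CRP) > 100 mg/dL", with IL-6 and ferritin as alternatives. The full marker condition is "either C Reactive Protein (CRP) > 100 mg/dL or IL-6 > 6 pg/mL or ferritin > 900 ng/L".

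The Background explains why these markers appear. It treats D-dimer as the leading parameter for stratifying thromboembolic risk, "together with other inflammation index like C-reactive-protein, interleukin 6 (IL-6) and ferritin".

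The cut-offs are printed once. No other section of the protocol gives a reference range, an assay unit or a second version of them.

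**The concern.** Two of the three units look wrong, and they err in opposite directions. The ferritin limb becomes practically always true and the CRP limb practically never true. With the limbs joined by *or*, the ferritin limb alone settles the matter whenever ferritin has been measured. If it has not, practically only IL-6 decides.

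A condition attached only to the lower D-dimer band is there to select within that band. As printed it does not. The rule helps decide who undergoes femoral venous puncture, heparinisation, pulmonary artery catheterisation and repeated contrast injections (OCT procedure section). Staff can apply the text literally, so that the marker step is empty, or silently read other units, so that eligibility decisions depart from the protocol. In the first case the marker step does no work; in the second the enrolled Part A group may not match its written definition.

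**Working it through.** **Inputs from the protocol, Inclusion Criteria (part A):** "C Reactive Protein (CRP) > 100 mg/dL"; IL-6 above 6 pg/mL; "ferritin > 900 ng/L"; any one of the three suffices. The protocol shows no derivation of these cut-offs, so there is no figure of its own to reproduce.

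**Inputs assumed (not in the protocol):** ferritin 5 to 2000 ng/mL in adults; CRP 50 to 600 mg/L in patients of this kind.

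**Step 1, unit conversion.**
- Ferritin: 900 ng/L ÷ 1000 mL per L = 0.9 ng/mL.
- CRP: 100 mg/dL × 10 dL per L = 1000 mg/L.

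**Step 2, distance from the assumed ranges.**
- Ferritin: 5 / 0.9 = 5.6 and 2000 / 0.9 = 2222, so the cut-off lies 5.6 to 2222 times below the values. With a narrower assumption of 10 to 400 ng/mL: 10 / 0.9 = 11 and 400 / 0.9 = 444. Both ranges lie wholly above the cut-off.
- CRP: 1000 / 600 = 1.7 and 1000 / 50 = 20, so the cut-off lies 1.7 to 20 times above the values.

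**Step 3, the rule as printed.** In the 5 to 10 mcg/mL band the condition is CRP > 1000 mg/L, or IL-6 > 6 pg/mL, or ferritin > 0.9 ng/mL. Anyone with a measured ferritin in the assumed range passes, so the condition excludes practically no one whose ferritin is known.

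**Step 4, where another reading would change a decision.** Suppose, for illustration only, that ng/mL and mg/L were meant. The ferritin cut-off is then 1000-fold too low and the CRP cut-off 10-fold too high. If IL-6 exceeds 6 pg/mL, both readings admit the patient and cannot differ. If IL-6 is 6 pg/mL or lower, or not measured:

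| Ferritin | CRP | As printed | Illustrative units |
|---|---|---|---|
| > 900 ng/mL | any or missing | in | in |
| > 0.9 to 900 ng/mL | > 100 mg/L | in | in |
| > 0.9 to 900 ng/mL | ≤ 100 mg/L or missing | **in** | **out** |
| ≤ 0.9 ng/mL or missing | > 1000 mg/L | in | in |
| ≤ 0.9 ng/mL or missing | > 100 to 1000 mg/L | **out** | **in** |
| ≤ 0.9 ng/mL or missing | ≤ 100 mg/L or missing | out | out |

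The readings disagree in two rows. How many patients fall in either cannot be obtained from the protocol.

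**The case against.** The strongest counter-argument is that no consequence is shown. The readings differ only for Part A patients in the 5 to 10 mcg/mL band whose IL-6 is low or unmeasured, and then only for certain ferritin and CRP combinations. The protocol says the study "will be conducted in 10 patients with mild-to-severe" ARDS, so the affected number could be zero. If IL-6 above 6 pg/mL already admits nearly everyone, correcting the units would restore no selection. Neither the sample size nor any described analysis uses these cut-offs. All this stands, and it limits the claim to the rule itself. It does not make the printed units right. With 10 patients, a single wrong entry would be 1/10 = 10% of the sample.

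Second, implausibility rests on laboratory ranges from outside the protocol. That is so, and they are marked as assumptions. For ferritin the conclusion is the same under both ranges tried; for CRP only one range was tried, and it lies wholly below the cut-off.

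Third, the two defects work separately. The loss of selection comes from ferritin alone; the CRP unit merely disables its own limb and matters only when ferritin is missing. This is correct.

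Fourth, a letter may have been lost when the PDF was read. That cannot be fully excluded for ng/L, but a dropped letter would not explain mg/dL, and the other units in the same criteria are intact.

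**Conclusion.** The concern holds. Both conversions are exact and nothing elsewhere in the protocol corrects the cut-offs. Read literally, the marker condition for the 5 to 10 mcg/mL band is met by practically anyone with a measured ferritin, while the CRP limb is practically inert.

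Confidence is high for the units and the logic, given the assumed ranges. It does not extend to any effect on enrolment, which is unquantified and may be nil, or to which units the sponsor intended. The other Part A criteria (severe disease, suspected MicroCLOTS, negative CT) still apply. The error should be fixed because it sits in an eligibility rule for an invasive procedure.

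**What to change.** The sponsor should check the ferritin and CRP cut-offs against the units in which the laboratory reports these tests and correct the line by amendment. The choice of threshold is the sponsor's; none is proposed here. Anyone already enrolled through the 5 to 10 mcg/mL band should be rechecked against the corrected rule.

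The cost is a one-line amendment and that recheck. Eligibility through the band may narrow slightly (ferritin), widen slightly (CRP, where ferritin is missing), or stay the same if IL-6 already decides. While the line is open, the sponsor should also settle a separate small gap: a D-dimer of exactly 10 mcg/mL falls in neither route, because both limits are strict.

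### The OCT thrombus endpoint is reported by CT-labelled area, but the protocol does not mask the image reading to area or CT status

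*Protocol*

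**What the plan says.** The section on study design, sample size and statistical analysis states: "The study is an open label, prospective, interventional clinical study of the safety, tolerability and potential diagnostic value". It describes an exploratory proof of concept in 10 patients and no comparator arm.

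The Primary Endpoint section has two entries. The first is "Overall safety of OCT procedure in COVID-19 pneumonia patients". The second begins "Presence of microvascular pulmonary thrombosis at OCT assessment in COVID-19 patients, both in" and goes on to name the ground-glass and the healthy ventilated areas.

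The OCT procedure section fixes how areas are chosen: "The choice of the pulmonary arteries to be cannulated will be driven by" the ground-glass area on CT. The procedure is then repeated in a healthy area ("without ground glass appearance at CT scan) area in the same lung") and in both area types of the other lung. Patients enter part A or part B according to whether the contrast CT is negative or positive for pulmonary thrombosis.

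The protocol names no reader for the OCT images. It does not mention offline or coded reading, or masking to area or to part A/B. The operator is given the task of registering imaging-related events, but nobody is named for the thrombus reading.

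**The concern.** Whether an OCT frame shows thrombus is a judgement on an image. Whoever acquires the pullback knows whether it comes from ground glass or from healthy lung, and can know whether the CT was positive. If the same knowledge is present when the image is read for the endpoint, doubtful images can be settled by expectation.

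This matters because the study has no comparator arm. The healthy areas within each patient are its only internal reference. The Background says that microvascular thrombosis in these patients is unproven, and that detecting it could support more intensive anticoagulation. With 10 patients, a few equivocal calls can shape the picture.

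Who reads the images, and what they know while reading, is study conduct. It has to be settled before the first endpoint reading. A statistical analysis plan written later cannot restore masking once images have been read with the label known.

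**Working it through.** No figure in the protocol bears on masking, so there is none to reproduce. The check sets the passages side by side and then illustrates what label-dependent reading could do.

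**Passages side by side**

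1. Endpoint: presence of thrombosis, reported for two area types (Primary Endpoint).
2. Label: the area type is known at acquisition, because it determines which vessel is cannulated (OCT procedure).
3. Masking: the study is open label, and no separate rule is given for the reading (Study design).

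Together these leave the reading unprotected. They do not say that it will be done unmasked.

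**Number of pullbacks**

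10 patients (protocol) x 4 areas (two area types in each lung, protocol) x 1 pullback per area (assumed) = about 40, or 20 per area type.

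**Illustration 1: equivocal images**

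Assumed, not in the documents: 10 to 20% of pullbacks are equivocal; they are called positive 75% of the time in ground glass and 25% in healthy areas; there is no true difference.

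- False difference = (0.75 - 0.25) x 0.10 = 5 points, up to (0.75 - 0.25) x 0.20 = 10 points.
- In pullbacks: 0.05 x 20 = 1, up to 0.10 x 20 = 2 per area type.
- Pooled over equal numbers of areas, the call rate for equivocal images is (0.75 + 0.25)/2 = 50%. This equals a neutral call rate, so pooled prevalence does not move.

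**Illustration 2: misclassification**

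Observed rate = prev x Se + (1 - prev) x (1 - Sp). Assumed: equal true prevalence in both area types, and Se = Sp = 0.85 when masked. Let b be the shift caused by knowing the label.

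- Specificity falls by b in ground glass and sensitivity falls by b in healthy areas: false difference = (1 - prev) x b + prev x b = b. For b = 0.05 to 0.30 this is 5 to 30 points at any prevalence.
- Only ground glass is over-called: false difference = (1 - prev) x b.

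| True prevalence | b = 0.05 | b = 0.30 |
|---|---|---|
| 20% | 4 points | 24 points |
| 50% | 2.5 points | 15 points |
| 80% | 1 point | 6 points |

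- Both area types over-called equally: the two shifts cancel and the false difference is 0.
- b = 0: the false difference is 0. Bringing b towards 0 is what masking to area is for.

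The result depends wholly on assumed inputs. It shows that the mechanism could matter, not that it will.

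**The case against.** **No comparison is planned.** A reader might infer that the endpoint is to be compared between area types and that a planned difference is at risk of inflation. The protocol does not support that. It asks for presence in both area types and gives no contrast, test, hypothesis or effect size. The text under its Primary endpoint analysis heading covers safety only. This objection stands. What remains is that rates for the two area types, reported side by side, form a descriptive contrast, and each rate depends on the reading.

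**Open label describes the procedure.** An invasive procedure cannot be masked to its operator, and the term does not say how stored images are read. This also stands: the point rests on the protocol's silence, not on a declared unmasked reading.

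**The direction is unknown.** The protocol's aim is to look for thrombosis that CT does not show, and it nowhere predicts more thrombus in ground glass than in healthy lung. A reader who expects thrombosis everywhere could over-call in both area types and create no false difference. One might infer a bias towards the MicroCLOTS hypothesis in overall prevalence, but illustration 1 shows no such shift, and the documents give no basis for one.

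**Masking to area is incomplete.** Every patient is enrolled with suspected MicroCLOTS, so coding the files cannot hide that expectation. Nor does it supply criteria for calling a thrombus. Both limits stand.

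**Imprecision is larger.** With 0 of 10 patients positive, the two-sided 95% upper limit is 1 - 0.025^(1/10) = 30.8%. A shift of 1 to 2 pullbacks is small beside that. But a confidence interval does not cover bias, and this bias is cheap to reduce.

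**Conclusion.** The point holds in a limited form. A primary endpoint that depends on image judgement is reported by an area label known at acquisition, and the protocol does not keep that label, or the CT result, from the reading. The area-specific thrombus rates and any descriptive contrast between them are open to reader expectation.

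Direction and size cannot be derived from the documents. The figure of 5 to 10 points rests on assumed equivocal and call rates. The misclassification model, equally assumed, ranges from 0 to 30 points. No distortion of a formal test can be claimed, because none is planned, and no claim about overall prevalence is supported.

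This should be changed because the remedy is small and because the healthy areas are the study's only internal reference. It does not invalidate the study or affect its safety objective.

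**What to change.** Add to the protocol, before any endpoint reading takes place:

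- Each pullback is stored under a code that hides the patient, the CT result (part A or B) and the area type.
- The existing reader reads the coded pullbacks offline, in random order and after a delay. Where staff other than the operator of that case are already available at the site, one of them is preferred.
- That reading is locked and used for the primary endpoint. Area and CT result are unmasked only afterwards.
- Live viewing during the procedure for safety is unchanged.

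The cost is about one protocol sentence and a few hours of file coding for roughly 40 pullbacks. The sample size and the procedure do not change. There are two downsides: the primary reading is not available live in the catheter laboratory, and a reader who was also the operator may recall some images and so be partly unmasked. Random order and delay reduce that recall but do not remove it.
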